5.7 Statistical models

5.7.1 Primary analysis

The following MMRM ANCOVA will be used for trough FEV₁:

Dependent variable = intercept + treatment + region + baseline FEV₁ + smoking status at screening + severity of airflow limitation + run-in post-bronchodilator FEV₁ + visit + treatment*visit + baseline value*visit + error.

The within-patient correlation will be modeled using an unstructured covariance matrix in the mixed model. The Kenward-Roger approximation will be used to estimate denominator degrees of freedom ([Kenward and Roger, 1997](#)).

If the model fails to converge with unstructured covariance matrix, either a compound symmetry (first choice) or first order autoregressive (AR1) (second choice) covariance structure will be used. For the efficacy IA, if the model still fails to converge only data up to week 12 will be included.

The SAS procedure PROC MIXED will be used for analysis. Results will be presented with LSM and standard error (SE) for treatment effects and LSM, SE, associated two-sided 90%

confidence interval, and two-sided p-value for treatment contrasts of each QBW251 dose versus Placebo.

• **MCP-Mod**

The Multiple Comparison Procedure – Modelling (MCP-Mod) methodology (see [Bretz et al 2005](#) and [Pinheiro et al 2014](#)) will be employed to assess the primary objective. The following steps for the MCP-Mod methodology will be performed. The analysis will be implemented in SAS (used for MMRM) and R (MCP-Mod) using DoseFinding R package:

Step 1 (Testing an overall dose-response signal - MCP part):

- a. Fit MMRM model. Extract estimates and variance-covariance matrix at Week 12 from fitted model.
- b. Perform multiple contrast test with pre-defined model types and optimal contrasts, using variance-covariance matrix at Week 12 from the MMRM.

Consider the following candidate models:

- Emax (ED50=25)
- Emax (ED50=75)
- Emax (ED50=150)
- sigEmax (ED50=25, h=3)
- sigEmax (ED50=75, h=3)
- sigEmax (ED50=150, h=3)
- exponential (delta=75)
- exponential (delta=150)
- linear

Present T-statistics and corresponding adjusted p-values for each candidate model.

If there is at least one significant DR relationship, the DR signal is declared and Step 2 will be performed.

Step 2 (Estimation of the dose-response curve and target dose – Mod part):

- a. Draw bootstrap samples (at least 1000) from a multivariate normal distributions $N(\mu, \sigma)$ with parameter μ and σ populated with the corresponding estimates and variance-covariance from the MMRM of step 1a. Fit each of the pre-defined models to the data of each sample. Select the model with the best fit based on generalized AIC and predict the dose-response curve with this model in each sample.
- b. Derive median and other quantiles for predicted response over the dose range from the bootstrap samples. This will result in an averaged model.
- c. Estimate the target dose(s): the smallest dose which shows a clinical relevant effect of delta for each of the bootstrap samples using the best model. The target dose will be

estimated for a delta of 50ml using inverse regression techniques (Bretz et al 2005). The averaged target dose is the median of the target doses over the bootstrap samples. The averaged target dose will only be derived if the estimated target dose of at least 50% of the bootstrap samples is within the investigated dose range.

• **Multiple imputation for supplementary analysis**

For supplemental analysis the following imputation steps need to be performed for missing data.

Off-treatment values will be considered for the analysis for patients discontinuing treatment not related to COVID-19, regardless of reason for discontinuing study.

- a) The following table provides an overview of the imputations rules for data after discontinuation:

	Discontinuation of study	
Discontinuation of study treatment	COVID-19-related	Non-COVID-19 related
COVID-19-related	no off-treatment data, MAR	no off-treatment data, MAR during follow-up, J2R/MAR after study discontinuation
Non-COVID-19 related	off-treatment data, J2R/MAR	off-treatment data, J2R/MAR
J2R/MAR: Missing data after discontinuation of study treatment will be imputed using J2R assumption for the QBW251 arms and MAR assumption for placebo arm.		

- b) Any other event leading to missing data prior to completion or discontinuation of study treatment: on-treatment value. Missing data will be multiply imputed based on the MAR assumption.

A patient can have missing data for both situations a and b.

1. For patients discontinuing double-blind treatment prematurely due to COVID-19 set off-treatment values to missing after COVID-related discontinuation.
2. Impute missing data using MAR:

Select all patients, impute missing values at Week 4, 8, 12, 16, 20 and/or Week 24 using the MI approach based on the fully conditional specification (FCS) method for 100 time and obtain 100 imputed dataset. Missing Week 4 values will be imputed separately for treatment group using a model with the imputed values of baseline FEV₁, region, smoking status, run-in pre-bronchodilator FEV₁ and severity of airflow as predictors. Missing Week 8 values will be imputed separately for each treatment group using a model with the imputed values of Week 4, baseline FEV₁, region, smoking status, run-in pre-bronchodilator FEV₁ and severity of airflow as predictors. Repeat the same for subsequent visits.

This results in 100 imputed datasets.

For patients in the QBW251 treatment groups who discontinued double-blind treatment prematurely not related to COVID-19, set imputed values after discontinuation of treatment to missing, as these will be imputed using J2R in step 3.

For patients in the QBW251 treatment groups who discontinued double-blind treatment prematurely related to COVID-19 and discontinued study not related to COVID-19, set imputed values after discontinuation of study to missing, as these will be imputed using J2R in step 3.

3. Impute missing for patients in the QBW251 treatment groups using J2R:

Select all patients, impute missing values at Week 4, 8, 12, 16, 20 and/or Week 24 using the MI approach, under assumption of missing not at random (MNAR) that patients in QBW251 treatment groups will behave as patients treated with Placebo, based on the fully conditional specification (FCS) method for 100 time and obtain 100 imputed dataset. Missing Week 4 values will be imputed using a model with the imputed values of baseline FEV₁, region, smoking status, run-in pre-bronchodilator FEV₁ and severity of airflow as predictors. Missing Week 8 values will be imputed using a model with the imputed values of Week 4, baseline FEV₁, region, smoking status, run-in pre-bronchodilator FEV₁ and severity of airflow as predictors. Repeat the same for subsequent visits.

This results in 100 imputed datasets.

4. Merge datasets from step 2 and step 3.

- a. For patients in QBW251 treatment groups discontinuing double-blind treatment prematurely not related to COVID-19 take imputed values after discontinuation of treatment from step 3.
- b. For patients in the QBW251 treatment groups who discontinued double-blind treatment prematurely related to COVID-19 and discontinued study not related to COVID-19, take imputed values after discontinuation of study from step 3.
- c. For all other missing (including those for Placebo patients) values take imputed values from step 2.

5. Week 12 data of the final multiply-imputed dataset where all missing values are filled will be analyzed (by imputed dataset) using a linear mixed model with treatment, region, smoking status at screening, run-in pre-bronchodilator FEV₁, severity of airflow limitation and baseline FEV₁ as predictors.

6. The results for the treatment effect from the 100 datasets will then be combined using Rubin's rule.

Step 1 to 4 will be implemented before MCP-Mod is used.

Step 5 and 6 will be used within MCP-Mod for step 1a Step 1b and 2a of the MCP-Mod will use the combined estimate and variance-covariance matrix of step 6..

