2.5.3 Handling of missing values/censoring/discontinuations

Since the estimand is related to an effect outside of rescue med intake, spirometry measurements within 6 hours of rescue medication or within 7 days of intake of SCS use will be set to missing. If one of the values contributing to the trough FEV₁ variable is missing at a visit, the remaining non-missing value will be taken as trough FEV₁. If both values are missing, then their trough FEV₁ will be regarded as missing at that visit.

For the primary analysis, only on-treatment data (from date of first randomized dose up to 1 day after date of last randomized dose) will be used as the estimand specifies a hypothetical on-treatment effect. Missing on-treatment data will not be explicitly imputed as the MMRM model implicitly imputes missing data assuming the missing at random (MAR) mechanism.

The imputation procedure(s) related to the trough FEV₁ supportive analyses ([Section 2.5.4](#)) are "jump-to-reference" (J2R) and MAR ([Carpenter et al 2013](#)). The imputations will be based on all available data (i.e. from all scheduled time points) using all covariates as specified in the MMRM. For J2R, only placebo (reference) data will be used. For MAR, data from the same treatment arm will be used for building the imputation model. Imputation of intermittent missing observations before treatment discontinuation will be carried out following a MAR mechanism for all treatment arms. Additional details are provided in [Section 5.7](#).

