2.5.4 Supportive analyses

A supplementary analysis will be performed that quantifies the treatment effect in all randomized patients during stable periods (i.e. outside episodes of COPD worsening that require rescue medication or SCS) with an adherence to treatment like we would see in clinical practice in a world without COVID-19, with the following post-randomization events accounted for by assessing:

- a. Intake of rescue medication or systemic corticosteroid: effect outside of periods of worsening disease that necessitate rescue med or systemic corticosteroid
- b. Discontinuation of study treatment for non-COVID-19 related reason with follow-up: actual off-treatment value. If no data was retrieved after study treatment discontinuation, missing data will be multiply imputed based on placebo arm data: J2R assumption for the QBW251 arms and MAR assumption for placebo arm.
- c. Discontinuation of study treatment due to a COVID-19 related reason: on-treatment value. Missing data will be multiply imputed based on the MAR assumption.
- d. Discontinuation of study participation due to any non-COVID -19 related reason: off-treatment value. Missing data will be multiply imputed based on placebo arm data: J2R assumption for the QBW251 arms and MAR assumption for placebo arm.

- e. Any other event leading to missing data prior to completion or discontinuation of study treatment: on-treatment value. Missing data will be multiply imputed based on the MAR assumption.

Results will be presented similarly to those of primary analyses.

Details are provided in [Section 5.7](#).

A supportive analysis will be performed including the 450mg dose and only data up to week 12. This will be done similarly as the primary analysis, however in addition candidate curves Emax(ED50=300), SigEmax(ED50=300) and Exponential(delta=300) will be considered.

A supportive exposure-response analysis may be performed outside the CSR.

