5.2 Visit windows

In general, if two consecutive visits V_t and V_s are x days apart, the upper limit of the visit window for V_t will be $V_{t+x/2}$ and the lower limit for the visit V_s will be $V_{s-x/2}$ (if x is even, the lower limit for V_s will be $V_{s-x/2}+1$, and the upper limit for V_t will be $V_{t+x/2}$). The algorithm needs to ensure that visit windows are not overlapping and that there are no gaps, such that each assessment can be uniquely allocated to one visit window.

For ECG and spirometry assessments, unplanned visits will be ignored for the windowing as scheduled timing is not available. If there are multiple assessments within a visit window with different scheduled time points, the one with the planned scheduled time points of the target day will be used; if scheduled time points are the same, the visit closer to the target day will be used.

For all other assessments, unplanned visits will also be considered for assigning visit windows. If there are multiple assessments within a visit window the closest to the target day will be used.

Only on-treatment values will be considered for mapping of visit windows. For trough FEV₁ visit windowing will be performed twice, once for primary analysis considering on-treatment measurements, and once for supportive analysis considering all post-baseline measurements whether being on-treatment or not.

The below table presents the visit windows for the respective assessments.

Analysis visit	Scheduled Day	Visit window – assessments a)	Visit window – assessments b)	Visit window – assessments c)	Visit window – assessments d)	Visit window – assessments e)
Day 1 post dose	Day 1	Day 1 (post-dose) - Day 7				

Week 2	Day 15	Day 8 - Day 22	Day 1 (post dose) - Day 22			
Week 4	Day 29	Day 23 - Day 43	Day 23 - Day 43	Day 2 - Day 43		
Week 8	Day 57	Day 44 - Day 71	Day 44 - Day 71	Day 44 - Day 71		
Week 12	Day 85	Day 72 - Day 99	Day 72 - Day 99	Day 72 - Day 99	Day 2 - Day 127	
Week 16	Day 113	Day 100 - Day 127	Day 100 - Day 127	Day 100 - Day 127		
Week 20	Day 141	Day 128 - Day 155	Day 128 - Day 155	Day 128 - Day 155		
Week 24	Day 169	Day 156 - Day 183	Day 156 - Day 183	Day 156 - Day 183	>Day 127	> Day 1
Follow-up	Day 197	>= Day 184	>= Day 184	>= Day 184		
a) ECG b) Vital signs c) Spirometry, Hematology, Chemistry, Urinalysis d) SGRQ, PGI-S, CASA-Q e) Weight, smoking status, XXXXXXXXXX						

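### SAP 5.7.1 step 2 fills on-treatment gaps from a model fitted partly to off-treatment FEV₁; if the QBW251 effect is lost after stopping, these values come out slightly too low

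*SAP*

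**What the plan says.** **Target.** SAP 2.5.4 item c assigns an on-treatment value, imputed under MAR, to patients who stop study treatment for a COVID-19 related reason. Item e does the same for the remaining gaps: "Any other event leading to missing data prior to completion or discontinuation of study treatment: on-treatment value". Items b and d, for non-COVID discontinuation, target the off-treatment value.

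**Data kept.** SAP 5.7.1 states: "Off-treatment values will be considered for the analysis for patients discontinuing treatment not related to COVID-19, regardless of reason for discontinuing study". Step 1 removes off-treatment values for one group only: "For patients discontinuing double-blind treatment prematurely due to COVID-19 set off-treatment values to missing after COVID-related discontinuation". SAP 5.2 windows the data for this purpose "once for supportive analysis considering all post-baseline measurements whether being on-treatment or not".

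**Model.** Step 2 reads "Select all patients, impute missing values at Week 4, 8, 12, 16, 20 and/or Week 24 using the MI approach based on" fully conditional specification, separately by arm. For example: "Missing Week 8 values will be imputed separately for each treatment group using a model with the imputed values of Week 4", plus baseline covariates. It has no treatment-status term. SAP 2.5.3 agrees: "The imputations will be based on all available data (i.e. from all scheduled time points) using all covariates as specified in the MMRM", and "For MAR, data from the same treatment arm will be used for building the imputation model".

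**Use.** After step 2, some imputed values in the QBW251 arms are deleted and replaced by jump-to-reference (J2R) values from step 3. Step 4c takes every other missing cell, placebo included, from step 2.

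**The concern.** The estimand and the algorithm aim at different quantities. A QBW251 patient who stops because of COVID-19, or who misses a visit while on drug, should receive a value typical of patients on drug. The regression that supplies it is fitted to a mixture: on-drug records, plus observed off-drug records of patients who stopped for other reasons and came back.

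The deletions after step 2 do not help. They remove imputed values only, and by then the retrieved off-drug observations have already shaped the fit.

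Step 3 assumes that QBW251 patients behave like placebo patients once they stop. On that assumption, off-drug records pull the fitted on-drug level towards placebo. The supplementary estimate, which enters MCP-Mod through steps 5 and 6, would be pulled the same way. Better retrieval of discontinuers, normally a strength, makes the pull stronger.

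**Working it through.** **1. Which cells are affected**

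| Missing cell | Target (SAP 2.5.4) | Filled by | Off-treatment records in the fit? |
|---|---|---|---|
| COVID-19 treatment stop, still in study or left because of COVID-19 (c) | on-treatment | step 2 | yes |
| Gap before treatment ends (e, and other pre-discontinuation gaps) | on-treatment | step 2 | yes |
| QBW251, after non-COVID stop (b, d) | off-treatment | step 3, J2R | not at issue |
| Placebo, after non-COVID stop (b, d) | off-treatment | step 2 | yes, and they belong there |

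The first two rows, in the QBW251 arms, are the problem.

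**2. The plan's own figure.** With 854 patients, 20% dropout and allocation 2:1:1:1:2, the 300 mg and placebo arms each have 854 × 0.8 × 2/7 ≈ 195 patients. The SE of their difference is 200 × √(2/195) = 20.3 mL. One-sided 5% power for that pair alone is 90.6% at 60 mL and 79.5% at 50 mL. The full multiple-contrast test gives a minimum over the candidate curves of 92.4% and 81.6% with the 11 curves, or 92.1% and 81.1% with the SAP's nine. The plan states 92% and 81%, so it reproduces. It does not depend on step 2.

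**3. Inputs for the size**
- From the documents: maximum effect 60 mL, SD 200 mL; off-treatment means more than 1 day after the last dose (SAP 2.1.1.3); half-life 10 to 16 hours (protocol 4.2); spirometry every 4 weeks from Week 4.
- Assumed, because the documents do not give them: non-COVID stops of 10-30% by Week 24, spread evenly; 30-100% of these retrieved; COVID-19 stops of 3-10%; 3% intermittent missing; the whole effect lost off drug.

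**4. Formulas.** Let d be the proportion stopped for non-COVID reasons by the visit, r the retrieved fraction, and m the share of the arm filled under c and e.
- Off-treatment share of the observed data = d·r / (1 − m − d(1 − r)).
- Rough ceiling on the shift per filled cell = that share × 60 mL. The actual shift is smaller because earlier visits are predictors.
- Shift in arm mean = m × shift per filled cell.

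Example (20% stops by Week 24, so 10% by Week 12; all retrieved): 0.10 / (1 − 0.0754) = 10.8%, and 0.108 × 60 = 6.5 mL. In simulation the error is −4.62 mL as written and −0.06 mL with an on-treatment-only fit, a shift of −4.56 mL. The arm mean moves by 0.0754 × (−4.56) = −0.34 mL.

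**5. Results** (2,000,000 simulated patients in one QBW251 arm, six visits)

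| Non-COVID stops / retrieved / COVID-19 stops | Week | m | Off share | Ceiling, mL | Shift per cell, mL | Arm mean, mL |
|---|---|---|---|---|---|---|
| 10% / 30% / 3% | 12 | 4.3% | 1.6% | 1.0 | −0.6 | −0.03 |
| | 24 | 5.6% | 3.4% | 2.1 | −1.3 | −0.07 |
| 15% / 50% / 5% | 12 | 5.2% | 4.1% | 2.5 | −1.6 | −0.08 |
| | 24 | 7.4% | 8.8% | 5.3 | −3.5 | −0.26 |
| 20% / 100% / 10% | 12 | 7.5% | 10.8% | 6.5 | −4.6 | −0.34 |
| | 24 | 12.1% | 22.8% | 13.7 | −9.5 | −1.15 |
| 30% / 100% / 10% | 12 | 7.4% | 16.2% | 9.7 | −6.8 | −0.51 |
| | 24 | 11.8% | 34.0% | 20.4 | −14.3 | −1.69 |

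Variations on the 20% row:
- No drug effect: shift about 0 at both visits.
- A further 50 mL fall after stopping: arm mean −0.63 mL at Week 12 and −2.08 mL at Week 24.
- Visit correlation 0.5 or 0.9: arm mean at Week 12 −0.38 or −0.32 mL.

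Two other set-ups with correlation 0.7 and 15% non-COVID stops by Week 12 gave 3.5-7 mL and 6-8 mL per cell at Week 12. The treatment difference fell by 0.3-1.3 mL in the former; the arm mean fell by 0.6-0.9 mL in the latter. The extreme case (9-17% of the arm filled, plus a 50 mL fall) reached 13 mL per cell and 0.17 × 13 = 2.2 mL in the arm mean.

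**6. Limit on the remedy.** Removing off-treatment values from every step 2 fit would also remove them from the model for placebo cells under b and d. With 50% retrieval and a 50 mL fall after stopping, the error in those cells rises from about +41 to +50 mL. In a similar simulation the placebo-arm mean error rose from +1.8 to +3.2 mL, for a gain of about 1 mL in the drug arm.

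**The case against.** The plan is open about its method: protocol 12.4.3 and SAP 2.5.3 both say that all available data are used, and same-arm data for MAR. That is so, but it confirms the mixed fit. It does not explain how such a fit yields the on-treatment value that items c and e name.

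The assumed missingness may be high. Protocol Table 6-2 postpones spirometry until the rescue washout is met, and protocol 8.3.9 reschedules visits that fall within 7 days of systemic corticosteroids, so few values should need blanking. This stands, and it favours the lower end of the ranges. Blanked values also belong to item a, not item e. That stands too, though SAP 2.5.3 sends intermittent gaps before discontinuation to MAR, so step 2 fills them all the same.

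The size objection is the strongest: a shift of about 1 mL against a half-length of 26 mL would not change the reading of a dose-response curve. I accept that.

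A reader might infer that QBW251 values are always imputed too low, or that the primary result or the power is biased. The documents support neither. The shift needs a positive effect that is lost off drug, or worsening after stopping. The primary MMRM uses on-treatment data only.

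**Conclusion.** The mismatch is in the text: cells with an on-treatment target are filled from a model that includes off-treatment observations, and no section limits that model to on-treatment data. The consequence is conditional and small. If a 60 mL effect is lost after stopping, the affected Week 12 values are roughly 1-8 mL too low, more with heavier discontinuation or a further fall after stopping, and up to about 14 mL at Week 24. The QBW251 arm mean falls by about 1 mL or less at Week 12 in most scenarios and about 2 mL in extreme ones. With no effect and no worsening, the shift is zero.

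These sizes rest on assumed COVID-19 splits, retrieval rates and visit correlations. Only the supplementary analysis and its Week 24 repeat (SAP 2.7.1.3) are touched. This is a minor point, worth correcting because the change is cheap and brings the imputation into line with the stated estimand.

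**What to change.** For cells under items c and e, and for other gaps before treatment discontinuation, fit the step 2 MAR model to on-treatment records only. Set off-treatment values to missing for that fit, then restore the observed values of non-COVID discontinuers before steps 3-5. Alternatively, add a time-varying on/off-treatment indicator and impute these cells with it set to on-treatment.

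For placebo cells under items b and d, keep the retrieved off-treatment placebo data in the fit, because their target is the off-treatment value. State in SAP 5.7.1 which records feed which fit.

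Cost: one extra data step, a short addition to the SAP text, and a fit on slightly fewer records.

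### SAP 5.7.1 step 3 is labelled jump-to-reference but describes copy-reference imputation, so the supplementary trough FEV₁ estimate lies above the named one for doses with a positive effect

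*SAP*

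**What the plan says.** Protocol 12.4.3 and 12.4.4 and SAP 2.5.3 and 2.5.4 all name J2R for QBW251 patients with missing data after a discontinuation unrelated to COVID-19. On the fit, SAP 2.5.3 says "For J2R, only placebo (reference) data will be used". For the algorithm it sends the reader on: "Additional details are provided in" section 5.7. The table of imputation rules in SAP 5.7.1 keeps the label: "Missing data after discontinuation of study treatment will be imputed using J2R assumption for the QBW251 arms and MAR assumption for placebo arm".

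The algorithm follows in steps 1 to 6 of SAP 5.7.1:

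- Step 2 imputes everything under MAR, then blanks the QBW251 values that fall after the relevant discontinuation. Values before it stay in the data set.
- Step 3 carries the J2R heading and the assumption that "patients in QBW251 treatment groups will behave as patients treated with Placebo". It then works visit by visit: "Missing Week 8 values will be imputed using a model with the imputed values of Week 4, baseline FEV₁, region, smoking status" and further covariates, and likewise for later visits.
- Step 4 merges the two sets of imputations. Patients who stop treatment because of COVID-19 and later leave the study for another reason are handled as "no off-treatment data, MAR during follow-up, J2R/MAR after study discontinuation". For them the analysis will "take imputed values after discontinuation of study from step 3".
- The pooled result feeds the dose-response analysis: "Step 5 and 6 will be used within MCP-Mod for step 1a".

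SAP 2.7.1.3 repeats the supportive analyses at Week 24. SAP section 4, which lists changes from the protocol's analyses, mentions only the candidate curves.

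**The concern.** J2R means that after discontinuation the patient's expected value moves to the placebo mean. Earlier residuals are kept as deviations from the mean of the patient's own arm. Nothing in steps 1 to 6 makes that subtraction or removes on-treatment values from the predictors. A QBW251 patient whose Week 4 value contains a drug effect therefore looks to a placebo regression like a better-than-average placebo patient, and the regression predicts a better-than-average placebo value at Week 8 and later. That is copy reference.

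For an effective dose the difference goes in one direction, towards a larger effect. It enters MCP-Mod and the estimation of the dose reaching 50 mL, and it recurs at Week 24. Readers would be told that the effect after stopping was set to zero when it was not. Two programmers, one following the label and one the steps, would produce different results.

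**Working it through.** **Inputs from the documents.** Visits at Weeks 4, 8, 12, 16, 20 and 24; 854 patients without the 450 mg arm; allocation 2:1:1:1:2; SD 200 mL; 20% dropout; maximum effect 50 or 60 mL; target delta 50 mL; planned 90% CI half-length 26 mL for the placebo-adjusted curve (SAP section 3; delta from SAP 2.5.2).

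**The plan's own figure.** SAP Table 3-1 gives 92% power at 60 mL and 81% at 50 mL. With 854 × 0.8 = 683 patients, the minimum power over the candidate set is 92.3% and 81.5% with the protocol's 11 curves, and 92.1% and 81.2% with the SAP's 9. These inputs therefore reproduce the table. The plan gives no figure for the supplementary estimate.

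**Assumptions, because the documents are silent.** Residual correlation 0.5 to 0.8, AR(1) or compound symmetry (CS), the two fallback structures in SAP 5.7.1. Stops spread evenly over the 4-week intervals: 3.33% each (10% by Week 12, 20% by Week 24) or 6.67% each (20% by Week 12). Base case: constant effect, no retrieved off-treatment data, no COVID-19 stops.

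**Formulas.** Take a patient with on-treatment visits 1 to k, a later visit t, and placebo regression slopes b = S₁₁⁻¹s₁ₜ:

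- J2R mean = placebo mean at t + b′(own values − own-arm means)
- Step 3 as written = placebo mean at t + b′(own values − placebo means)
- Difference, on average = b′δ, where δ is the vector of drug effects at visits 1 to k

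The arm-level shift is the sum over stopping patterns of (share imputed) × b′δ.

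**Week 12, 50 mL, 20% stopped.** The 80% who remain contribute 0.8 × 50 = 40.0 mL, which is the J2R result. Each stopping pattern has a share of 0.0667.

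| Correlation | b′δ, stop before Week 4 | b′δ, Weeks 4–8 | b′δ, Weeks 8–12 | Shift (mL) | Estimate (mL) |
|---|---|---|---|---|---|
| AR(1) 0.5 | 0 | 0.25 × 50 = 12.5 | 0.5 × 50 = 25.0 | 2.50 | 42.5 |
| AR(1) 0.8 | 0 | 0.64 × 50 = 32.0 | 0.8 × 50 = 40.0 | 4.80 | 44.8 |
| CS 0.5 | 0 | 0.5 × 50 = 25.0 | (1/3 + 1/3) × 50 = 33.3 | 3.89 | 43.9 |
| CS 0.8 | 0 | 0.8 × 50 = 40.0 | (4/9 + 4/9) × 50 = 44.4 | 5.63 | 45.6 |

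**Other cases, same method.**

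| Case | J2R (mL) | As written (mL) |
|---|---|---|
| Week 12, 50 mL, 10% stopped | 45.0 | 46.2–47.8 |
| Week 24, 50 mL, 20% stopped | 40.0 | 41.6–47.5 |
| Week 12, 50 mL, 20% stopped, 25% of stops COVID-19-related (MAR) | 42.5 | 44.4–46.7 |
| Week 24, 50 mL, 20% stopped, 25% COVID-19-related | 42.5 | 43.7–48.1 |
| Week 12, effect building linearly to 50 mL, 20% stopped | 40.0 | 41.4–42.5 |
| Week 12, 60 mL, 20% stopped | 48.0 | 51.0–54.8 |
| Week 12, 60 mL, 10% stopped | 54.0 | 55.5–57.4 |

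If half of those who stop supply off-treatment values with zero effect, every shift halves. With 20% stopped it becomes 1.25–2.8 mL at Week 12 and 0.8–3.8 mL at Week 24. With zero true effect the shift is zero.

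**Simulation checks.** With 244 patients per arm (854 × 2/7), SD 200 mL and 3,000 replicates, a placebo-only sequential fit minus own-arm-centred J2R gave Week 12 shifts of 2.60, 4.83, 3.70 and 5.59 mL (Monte Carlo SE 0.12–0.14), in the row order of the first table. A separate large-sample run at 60 mL, 20% stopped and CS 0.7 gave 47.7 mL for J2R and 54.1 mL as written; the formulas give 48.0 and 54.1 mL.

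**The case against.** The strongest reply is that step 3 is under-specified, not wrong. It starts from all patients, does not say which arm's data fit the model, and does not mention centring either way. The plan's own account of J2R, a placebo-only fit and patients behaving like placebo, is compatible with step 3, and neither document defines the method further. A programmer who knows J2R might follow the heading.

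This does not rescue the text. J2R is a named method, SAP 2.5.3 points to section 5.7 for its details, and the regression given there, carried out as stated with the placebo-only fit, is copy reference. A fit pooled over all arms would not be J2R either. Its means would contain drug effect, so it would lie above J2R too.

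The points about size stand. The excess needs a stop after Week 4, for a reason unrelated to COVID-19, with no retrieved value, positive correlation and an effect already present. Protocol 9.1.1 asks patients who stop treatment to keep attending, and such data shrink the shift. The crossing of 50 mL at a 60 mL effect is fragile:

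- With a 25% COVID-19 share, J2R becomes 48.0 + 0.25 × 0.20 × 60 = 51.0 mL, and both methods exceed 50.
- With half retrieved, the written steps give 49.5–51.4 mL.
- With a linear build-up to 60 mL, they give 49.7–51.0 mL.

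One dose mean crossing 50 mL is also not the same as a changed target dose, which is a bootstrap median from fitted curves.

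**Conclusion.** The concern holds. As written, step 3 is copy reference under a J2R label, and the change of method is not declared. In the base case at 50 mL the Week 12 estimate is too high by 1.25–2.8 mL (10% stopped) or 2.5–5.6 mL (20% stopped), which is 5–22% of the planned 26 mL half-length. At Week 24 the excess is 1.6–7.5 mL. Retrieval, COVID-19-related stops and a gradual onset of effect all reduce it. Its direction for an effective dose depends only on positive within-patient correlation and an effect already present when patients stop; its size rests on the assumptions above.

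The primary MMRM, the behaviour under a flat dose-response and patients who stop before Week 4 are unaffected, and the written estimate still lies below the MAR one. It should be corrected because the reported method would not be the one performed, but it does not threaten the primary conclusion.

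**What to change.** Choose one of two.

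**(a) Make step 3 true J2R (preferred, as it matches the named estimand).** For example, use a joint multivariate normal model with covariate-adjusted own-arm visit means up to discontinuation and placebo means after it, drawn afresh for each imputation. State which mean applies to retrieved off-treatment values. State also which applies to the MAR-imputed follow-up values of patients who stop treatment for COVID-19 and later leave the study for another reason. The cost is new imputation code, rules for those two groups, and a slightly less favourable supplementary estimate for effective doses.

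**(b) Keep the algorithm and rename it.** Call it copy reference in SAP 2.5.3, 2.5.4 and 5.7.1, and list the departure from protocol 12.4.3 and 12.4.4 in SAP section 4. That entry is enough; changing the protocol text would need a formal amendment under protocol 14.1. The cost is wording, plus giving up the assumption of zero effect after stopping that the J2R label implies.

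In both cases, repeat in step 3 that the model is fitted to placebo patients only. Neither option needs new data.
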